Visual analogue scores for pain and for nausea, and FPS-R scores for pain and BARF scores for nausea will be examined for normal distribution by the Kolmogorov-Smirnov test, but it is anticipated that the distribution will not be normal. Descriptive statistics (mean, median, standard deviation, and frequency distribution) of the nausea and pain scores will be obtained. The incidence of postdischarge nausea will be determined from the responses recorded in the diary and in the follow up phone call. The construct validity of the BARF scale would be assessed using the assumption that antiemetics reduce nausea and therefore nausea scores would be lower in children after the administration of an antiemetic (hypothesis 1). A subgroup of patients who received rescue antiemetics in the PACU will be examined. The pretreatment and post treatment VAS scores for nausea and BARF scores will be compared using a Wilcoxon test for non Gaussian distributed data. A reduction of scores by 2 cm on the VAS scale for nausea is traditionally accepted as a clinically satisfactory therapeutic response. A significant reduction in the BARF scores by 1 face in such patients will be accepted as construct validation. Content validity would be assessed by testing the hypothesis is that children with nausea will score higher on these scales than children without nausea (hypothesis 2). We will compare the postoperative nausea scores in patients who received rescue antiemetic therapy with the scores in patients who did not require this therapy using the Mann Whitney test. In addition, we will compare preoperative and postoperative BARF and VAS scores for nausea in patients who received antiemetics, making the assumption that healthy children will be free from nausea in the preoperative area. The Wilcoxon test for non Gaussian distributed data will be used for this comparison. Convergent validity would be tested by examining the correlation between BARF and VAS scales for nausea using the Spearman's Rho test. The hypothesis tested is that there would be a good correlation between the two scales (hypothesis 3). Discriminant validity would be tested by examining the relationship between pain and nausea. The hypothesis tested is that there would be a poor correlation between pain and nausea scores, particularly after the administration of opioids for analgesia (hypothesis 4). The correlation between (1) VAS scores for pain and nausea and (2) pain scores using the FPS-R scale and nausea scores using the BARF scale will be determined. Discriminant validity would be accepted if the correlation between these scores is not as good as the correlation between (a) VAS score for pain and the FPS score, (b) VAS score for nausea and the BARF score. A subgroup of patients who received analgesic therapy in the PACU will be examined. The correlation between the change in pain scores and nausea scores with analgesic treatment will be examined using the Spearman's Rho test. We can anticipate that there will be some correlations between nausea and pain as patients with pain often have concomitant nausea. However, satisfactory treatment of pain with opioids may not reduce nausea but even increase it, as nausea is a side effect of such therapy. Similarly, the correlation between the change in pain scores and nausea scores with antiemetic treatment will be examined using the Spearman's Rho test. The hypothesis tested will be accepted if the correlation of VAS and FPS-R scores will differ from the correlation between VAS scores for nausea and BARF scores. P values below 0.05 will be considered statistically significant. The minimum clinically relevant change in BARF and VAS scores for nausea will be determined by calculating the change in scores for patients who rated their nausea to be a little better than before or a little worse than before. Similarly, the scores at which a patient felt the need for rescue therapy would be determined in those subjects who responded positively to a question "Do you want any treatment for your nausea?" This will provide the threshold score for patient perception of the need for rescue therapy. The first and subsequent scores obtained from subjects who rated their symptoms as "no change from before" will be examined using an intra-class coefficient >0.7 as the criterion for test / retest reliability.

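### Hypothesis 4, change scores: no usable acceptance criterion, because the named test looks at zero and the rule that follows contains no pain-nausea correlation

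*Combined protocol and SAP*

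**What the plan says.** All of this is in section G2 (Data Analysis) of the combined protocol and SAP, under discriminant validity.

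- **Hypothesis:** "there would be a poor correlation between pain and nausea scores, particularly after the administration of opioids for analgesia (hypothesis 4").
- **Rule for the scores themselves:** "Discriminant validity would be accepted if the correlation between these scores is not as good as the correlation between (a) VAS score for pain". The sentence goes on to pair pain VAS with FPS, and names nausea VAS with BARF as comparison (b).
- **Changes, children given analgesics:** "The correlation between the change in pain scores and nausea scores with analgesic treatment will be examined using the Spearman's Rho test".
- **Changes, antiemetics:** "the correlation between the change in pain scores and nausea scores with antiemetic treatment will be examined using the Spearman's Rho test".
- **Expectation:** "We can anticipate that there will be some correlations between nausea and pain as patients with pain often have concomitant nausea". The plan adds that "satisfactory treatment of pain with opioids may not reduce nausea but even increase it, as nausea is a side effect of such therapy".
- **Rule placed directly after the change-score sentences:** "The hypothesis tested will be accepted if the correlation of VAS and FPS-R scores will differ from the correlation between VAS scores for nausea". Its second correlation pairs nausea VAS with BARF.
- **Significance:** "P values below 0.05 will be considered statistically significant".

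Section G1 (Sample Size) gives 27 children for hypotheses 1 and 2, 127 for hypothesis 3, and nothing for hypothesis 4.

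**The concern.** The hypothesis speaks of the period after opioids in particular, and the change-score analyses are the part of the plan aimed at it. A hypothesis of poor correlation needs either a stated ceiling or a comparison with something that should correlate well. The change-score analyses have neither.

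Without one, whoever writes the report is left with a P value from a Spearman test. That P value answers whether rho is zero, which the plan does not claim. In a small subgroup a substantial pain-nausea link can look absent. In a large one, a weak link that the plan already expects can look like a failure of discriminant validity. The benchmark that would settle it, whether BARF changes track nausea VAS changes more closely than they track pain changes, is not planned.

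**Working it through.** **1. Which criteria could apply to the change correlations?**

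| Candidate in G2 | Correlations used | Can it judge the pain-change/nausea-change rho? |
|---|---|---|
| Not-as-good-as rule | Pain-nausea against VAS/FPS (pain) and VAS/BARF (nausea) | Right form, but stated for scores, before the change analyses, and not extended to changes |
| Will-differ-from rule, right after the change sentences | Pain VAS/FPS-R against nausea VAS/BARF | No: neither is a pain-nausea correlation. Two equally good scales would fail it, and one poor scale would pass it |
| Spearman test, P<0.05 | Pain-nausea change rho alone | Only against zero, if read conventionally; G2 states no null value |

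**2. The plan's own sample sizes (G1).**

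- 27: paired t test, two-sided alpha 0.01, difference 2.0 cm, 2.5 cm read as the SD of the change. The noncentrality is (2.0/2.5) × √27 = 4.16, giving power 0.905 (0.890 at n = 26). The figure reproduces.
- 127: Fisher z, lower limit 0.7, 99% confidence. [2.576/(atanh 0.8 − atanh 0.7)]² + 3 = [2.576/(1.0986 − 0.8673)]² + 3 = 127. The figure reproduces.

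Neither addresses hypothesis 4. After 10% dropout, 240 × 0.9 = 216 children remain. Reaching 27 given antiemetics would need 27/216 = 12.5% of them, a rate that the documents do not state.

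**3. What a test against zero does.** Two-sided 0.05 is assumed, as sidedness is not stated. The critical value is t/√(n − 2 + t²). At n = 27, t = 2.060, so it is 2.060/√(25 + 4.24) = 0.38.

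Simulated probability of a **non-significant** result (bivariate normal data, true Spearman rho as shown, 10,000 replicates):

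| n | rho 0.2 | rho 0.3 | rho 0.4 | rho 0.5 |
|---|---|---|---|---|
| 27 | 84% | 67% | 46% | 24% |
| 50 | 73% | 44% | 18% | 4% |
| 100 | 48% | 14% | 1.4% | 0% |
| 150 | 31% | 4% | 0.1% | 0% |
| 216 | 16% | 0.4% | 0% | 0% |

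If 0.4 and 0.5 are instead the Pearson correlations of the underlying normal variables, the n = 27 entries become about 49% and 28%. Only n = 27 is a planning figure. The sizes from 50 to 216 are assumptions that span what the analgesic subgroup could be.

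Reading the 0.2 column the other way, a weak rho of 0.2 is significant in 100 − 48 = 52% of trials at n = 100, 69% at 150 and 84% at 216.

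**4. What an interval would show at n = 27.** Fisher z with variance (1 + r²/2)/(n − 3). For r = 0.30, SE = √(1.045/24) = 0.209 and atanh 0.30 ± 1.96 × 0.209 runs from −0.10 to 0.72, so rho lies between −0.10 and 0.62. For r = 0 it lies between −0.38 and 0.38. Neither interval separates poor from moderate correlation.

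**5. Would a benchmark comparison work?** The table gives the power to show that the BARF/nausea VAS change correlation exceeds the pain-nausea one in the same children. It uses a Meng-type test of dependent correlations (4,000 replicates) as a stand-in for the bootstrap, for a single comparison. The true correlations are assumptions, because the documents give none for changes.

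| BARF/VAS vs pain-nausea | n = 27 | n = 50 | n = 100 |
|---|---|---|---|
| 0.8 vs 0.3 | 80% | 98% | 100% |
| 0.8 vs 0.5 | 56% | 85% | 99% |
| 0.7 vs 0.3 | 52% | 81% | 99% |
| 0.6 vs 0.3 | 28% | 50% | 82% |

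Requiring two such comparisons at once can only lower these figures.

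**The case against.** A reader might infer that the plan accepts discriminant validity whenever the change rho is non-significant. The text does not say so. It says that the correlations will be examined, it states no null value, and the P<0.05 sentence is a general convention. By expecting some correlation, the plan also shows that zero is not its hypothesis. The supportable claim is narrower: no usable criterion is given, and the only one left by default is a test of zero.

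A reader might also infer that both treated subgroups are small. That is not supported either. The 27 is a power requirement for the antiemetic hypotheses, not a forecast of how many will be treated, and it says nothing about children given analgesics. With 100 of them, a true rho of 0.4 would be missed in only about 1-2% of trials.

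Further, hypothesis 4 already has a sensible comparative rule for the scores, so its main conclusion does not rest on the changes. Nor is the evidence lost: section F2 collects all four scales before and 30-60 minutes after either treatment.

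These points limit the size of the problem and stand. They do not supply a criterion for the change scores, and the nearest rule compares the wrong pair of correlations. A large subgroup does not rescue the test of zero; it changes the direction of the error.

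**Conclusion.** The concern holds in a limited form. For the change-score part of hypothesis 4, following G2 as written can neither support nor refute a poor pain-nausea correlation. The will-differ-from rule does not involve that correlation, and a test of zero addresses a claim that the plan does not make.

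The size depends on how many children are treated. At 27, a true rho of 0.4 goes undetected in about 46-49% of trials. At 100 to 216, a rho of 0.2 is declared significant in about 52-84%. These figures assume a two-sided test at 0.05 and bivariate normal data; ties on a faces scale would alter them somewhat. The rule for the scores themselves is not affected by this gap. This is a cheap improvement, not a threat to the study's main validity claim.

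**What to change.** In G2, for change scores, replace the will-differ-from rule with the following:

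1. In the analgesic and antiemetic subgroups separately, compute rho(change BARF, change nausea VAS), rho(change FPS-R, change pain VAS) and the pain-nausea change rho. Name the scale pairs for the last; the two already used for the scores (VAS with VAS, FPS-R with BARF) can be carried over.
2. Report each same-symptom rho minus the pain-nausea change rho, with a 95% bootstrap interval that resamples children, and give the number of children in each subgroup.
3. Claim discriminant validity for changes only if the lower limits exceed zero.
4. Show the pain-nausea change rho itself, with its sign and interval. The plan allows that nausea may rise as pain falls, and a large negative rho would otherwise be hidden inside a favourable difference.
5. State that a non-significant pain-nausea rho is not by itself evidence for the hypothesis.

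The cost is a paragraph of analysis text and a short bootstrap on data already collected. The downside is that with few treated children the interval may be too wide to support the claim, and the report must then call the result inconclusive.

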Pediatric research in the management of nausea has been limited by the absence of a reliable method to quantify the intensity of this subjective symptom. In adults, the visual analog scale (VAS) is an accurate tool, but this has not been shown to be reliable in young children. A scale is a series of points made on a line that will be used for measurement; a mark on the far left of the line shows little pain and the mark on the far right means a lot of pain. By default the most common objective outcome measure used in pediatric studies has been the incidence and number of emetic episodes. This measure, however, correlates poorly with the somatic subjective symptom of nausea. Apfel et al have shown that 30-40% of adult patients undergoing surgery have post discharge nausea and / or vomiting while 12% have vomiting. These data on nausea in adults were based on a visual analog scale for nausea. There are no data on the incidence of postoperative nausea in children since the severity of symptoms are difficult to measure as younger children are known to be unable to use the VAS reliably. Recently a pictorial scale for measuring nausea, the Baxter Animated Retching Faces (BARF) scale, has been developed and shown to have construct, content and convergent validity as an instrument to measure nausea in children. This was a two center study that was limited to children who could speak English. The clinical usefulness of this scale in determining the incidence of postoperative and post-discharge nausea in children has yet to be determined including the lowest age where it can be used reliably, the score associated with a patient's perception of a need for treatment, the minimum change in the scores of clinical relevance and the test-retest reliability when nausea is rated as not having changed. The score has also not been validated in children who speak Spanish. This study is designed to provide the missing information and will specifically look at the Spanish speaking population.

Section D: Purpose and Objectives

This study in the pediatric Spanish speaking patient population is designed to determine: (1) The validity of the scale to measure nausea in Spanish speaking children (2) the incidence of postoperative nausea as compared to postoperative vomiting in the Post Anesthetic Care Unit (PACU) and on discharge (Post Discharge nausea and Vomiting) in this population (3) The minimal clinically relevant differences in nausea on

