The power analysis was calculated conservatively for the following hypotheses:

Hypothesis 1: Nausea scores on the BARF and VAS scales would be lower in children after the administration of an antiemetic. A reduction in the VAS by 2 cms and by 1 face on a faces scale is considered a clinically important reduction in symptoms. (13) Assuming that the SD of nausea on the VAS scale in children is similar to that in adults (2.5 cm) (14), a sample size of 27 would have a 90% power at the 0.01 level of significance in detecting a 2.0 cm difference in the VAS following antiemetic therapy. Hypothesis 2: Children who received rescue antiemetics in the postoperative period will have higher postoperative nausea scores on the BARF and VAS scales than those who did not receive rescue antiemetics. In addition, children who required rescue antiemetics will have higher nausea scores at the time they received the rescue drug in the postoperative period than before they developed nausea. In other words, nausea scores in the postoperative period will be higher than scores prior to induction of anesthesia in children who received rescue antiemetics. (12) The power analysis for hypothesis 2 is similar to that for hypothesis 1, and a sample size of 27 would have a 90% power at the 0.01 level of significance in detecting a 2.0 cm difference in the VAS.

Hypothesis 3: There will be a good correlation between the BARF and VAS scores for nausea. A sample size of 127 would be estimated for an estimated maximum r of 0.8, a half-width of the confidence interval of ± 0.1 at an alpha of 0.01. (15) These estimates of r are in keeping with previous studies of the correlation between

pain scores on the VAS and the FPS-R scales. (6)

Allowing for a 10% rate of dropouts and incomplete data, we plan to recruit 240 patients in the preoperative area for the study to obtain data to test all hypotheses.

G2. Data Analysis

Provide a description of your plan for data analysis. State the types of comparisons you plan (e.g. comparison of means, comparison of proportions, regressions, analysis of variance). Which is the PRIMARY comparison/analysis? How will the analyses proposed relate to the primary purposes of your study?

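### Section G2 gives two unreconciled acceptance rules for discriminant validity (hypothesis 4), and the second has no direction and, read naturally, no pain–nausea correlation

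*Combined protocol and SAP*

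**What the plan says.** All the relevant analysis text is in Section G2 (Data Analysis) of the combined protocol and SAP.

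- **The hypothesis.** "The hypothesis tested is that there would be a poor correlation between pain and nausea scores". It is numbered hypothesis 4 and is expected to hold particularly after opioids.
- **The labelled rule.** Two pain–nausea correlations are to be computed: VAS with VAS, and FPS-R with BARF. Then: "Discriminant validity would be accepted if the correlation between these scores is not as good as the correlation between" pain VAS and FPS, and between nausea VAS and BARF.
- **The change-score analyses.** In children given analgesics in the PACU, "The correlation between the change in pain scores and nausea scores with analgesic treatment will be examined" by Spearman's rho. A parallel analysis follows for antiemetic treatment.
- **The closing rule.** Directly after these, the hypothesis tested is to be "accepted if the correlation of VAS and FPS-R scores will differ from the correlation between VAS scores for nausea and BARF scores". The 0.05 significance threshold comes next.

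Section G1 sizes hypothesis 3, not hypothesis 4: "A sample size of 127 would be estimated for an estimated maximum r of 0.8". It adds that "These estimates of r are in keeping with previous studies of the correlation between" pain VAS and FPS-R. Section D lists as its first objective "The validity of the scale to measure nausea in Spanish speaking children".

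**The concern.** Discriminant validity asks whether a nausea scale measures something other than pain. The quantity that decides this is the correlation between pain and nausea scores. The labelled rule uses it and points the right way. The closing rule, on its natural reading, sets one same-symptom correlation against another, so it compares two pieces of convergent evidence. It is met whether the nausea pair is better or worse than the pain pair, and it stays the same however strongly BARF follows pain.

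The plan does not say whether the closing rule replaces the labelled rule, restates it, or applies only to the change scores. It names no method for comparing correlations under either rule. An analyst following the text could therefore report either verdict from the same data, and could choose between them after seeing the results. Scale validity is the study's first objective, and discriminant validity is one of the four kinds of validity that G2 tests.

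**Working it through.** **1. The terms in each rule**

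| | Labelled rule | Closing rule |
|---|---|---|
| Pain VAS with FPS-R | comparator | first term |
| Nausea VAS with BARF | comparator | second term |
| Pain with nausea | quantity judged | absent |
| Direction | pain–nausea lower | none |
| Method of comparison | none named | none named |

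**2. The plan's own expected correlation**

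G1 gives n = 127 for r = 0.8, half-width 0.1, alpha 0.01. By Fisher's z, atanh(0.8) = 1.099 and 2.576/√(127 − 3) = 0.231. The limits are tanh(1.099 − 0.231) = 0.700 and tanh(1.099 + 0.231) = 0.869. The lower half-width is 0.100, so the figure reproduces (a strict search gives 128). G1 supports this r by pointing to earlier pain VAS/FPS-R correlations. If both scales behave as planned, the two terms of the closing rule are about equal and that rule should not be met.

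**3. Illustrative simulation**

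Inputs from the plan: same-symptom r = 0.8; n = 240 × 0.9 = 216; n = 127; threshold 0.05. All other correlations are assumptions.

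Method: four normal scores per child (pain VAS, FPS-R, nausea VAS, BARF), with target Spearman values converted to Pearson by 2·sin(πr/6) and all pain–nausea correlations set equal. There were 500 studies at n = 216 and 600 at n = 127, each with 300 bootstrap resamples of children. The closing rule counts as met if the 95% interval for rho(pain VAS, FPS-R) − rho(nausea VAS, BARF) excludes 0. The labelled rule counts as met if the lower limits of all four differences (same-symptom minus pain–nausea) exceed 0.

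Percentage of studies meeting each rule (labelled / closing):

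| Pain pair | Nausea pair | Pain–nausea | n = 216 | n = 127 |
|---|---|---|---|---|
| 0.8 | 0.8 | 0.1 | 100 / 5.8 | 100 / 5.5 |
| 0.8 | 0.8 | 0.3 | 100 / 6.2 | 100 / 5.7 |
| 0.8 | 0.8 | 0.8 | 0 / 6.0 | 0 / 3.0 |
| 0.8 | 0.5 | 0.3 | 66 / 100 | 39 / 98.5 |
| 0.8 | 0.5 | 0.5 | 0 / 100 | 0 / 99.3 |
| 0.8 | 0.9 | 0.3 | 100 / 91 | 100 / 71 |

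Monte Carlo error is about 2 points on the 5–6% entries. In the first three rows discrimination goes from clear to absent, and the closing rule stays near its false-positive rate. In the fifth row BARF is no closer to nausea VAS than to the pain scales, yet the closing rule is almost always met.

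**4. A second method**

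This used a Steiger-type test of two dependent correlations for the closing rule, point estimates for the labelled rule, and 2000 studies at n = 216. With correlations of 0.8, 0.8 and 0.1 (same order), the labelled rule is met in 100% and the closing rule in 7%. With 0.9, 0.75 and 0.80, the labelled rule is met in about 1% and the closing rule in 100%. The two rules give opposite verdicts in both directions.

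**5. If *differ* means only that the two estimates are unequal**

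With both true values at 0.8, the sample correlations differ at two decimals in roughly 84–97% of studies across runs and sample sizes. On that reading almost any result is accepted.

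**The case against.** **The first VAS in the closing rule is unlabelled.** If it means nausea VAS, the rule compares a pain–nausea correlation with the nausea pair. A simulation of that reading (n = 216, same-symptom r = 0.8, 150 studies) is met in 100%, 100% and 3% of studies at pain–nausea correlations of 0.1, 0.3 and 0.8, so it does discriminate. The text points the other way. FPS-R is a pain scale, both the labelled rule and G1 pair it with pain VAS, and only the second VAS in the sentence is marked as nausea. On either reading the sentence has no direction and is not reconciled with the labelled rule.

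**A sound rule is already present.** The labelled rule is directional and names the right correlations, and the closing sentence may concern only the change scores. This limits the damage, because the needed correlations are computed anyway. But the plan does not say that the labelled rule governs. If the closing rule covers only change scores, then the analyses that address the opioid part of hypothesis 4 are left with a criterion that cannot answer it.

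**The percentages depend on choices the plan does not make.** This stands. Requiring confidence intervals for the labelled rule matters in small samples: at an assumed treated subgroup of 27, with correlations of 0.8, 0.8 and 0.3, that rule is met in about 45% of studies with intervals and 99% on point estimates. The scores were also simulated as normal, although the plan expects otherwise. The logical point needs none of these figures.

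**Conclusion.** The concern holds. G2 states two acceptance rules for the same hypothesis without saying how they relate. The closing rule has no direction and, on its natural reading, omits the correlation that hypothesis 4 is about. Followed literally, it would usually reject discriminant validity when both scales perform as G1 expects (met in about 6% of studies at n = 216), and it would accept it when BARF tracks nausea VAS no better than it tracks pain (met in 100% at 0.8, 0.5 and 0.5). These sizes assume a two-sided 0.05 comparison and correlations that, apart from 0.8, are not in the documents.

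This should be corrected before analysis. It does not undermine the study, because a usable rule is already in the plan and the data to apply it are already to be collected.

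**What to change.** Replace the closing sentence, rather than delete it, so that one rule governs both scores and change scores. For example:

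> Hypothesis 4 will be supported if each pain–nausea correlation (VAS with VAS, FPS-R with BARF) is lower than both same-symptom correlations (nausea VAS with BARF, pain VAS with FPS-R).

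Add two details:

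- **Method.** Estimate each difference with a confidence interval, using a method for correlations measured in the same children, such as a bootstrap that resamples children or a test for dependent correlations. State whether acceptance rests on the interval or on the point estimate.
- **Deciding analysis.** Name the analysis set and time point that decide hypothesis 4. If intervals are required, treated subgroups may be too small to decide it and would be better reported as supportive.

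The cost is one replaced sentence plus these specifications in G2. No new data or visits are needed, and the sample size of 127 for hypothesis 3 is unaffected.

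### Does sizing hypotheses 1 and 2 at the 0.01 level but testing them at 0.05 call for a change to the plan?

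*Combined protocol and SAP*

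**What the plan says.** Section G1 (Sample Size) introduces its calculations with "The power analysis was calculated conservatively for the following hypotheses". For hypothesis 1 (nausea scores fall after an antiemetic) it takes a 2.0 cm VAS difference and an adult SD of 2.5 cm, and concludes that "a sample size of 27 would have a 90% power at the 0.01 level of significance". For hypothesis 2 (children given rescue antiemetics score higher than others, and higher than they did before induction) it says "The power analysis for hypothesis 2 is similar to that for hypothesis 1" and repeats the 27. G1 does not name the test, the sidedness, or whether 2.5 cm is the SD of a single score or of a difference. It plans to recruit 240 children, allowing 10% for dropout and incomplete data.

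Section G2 (Data Analysis) tests hypothesis 1 as follows: "The pretreatment and post treatment VAS scores for nausea and BARF scores will be compared using a Wilcoxon test". For hypothesis 2 it uses a Mann-Whitney test between rescued and non-rescued children and a Wilcoxon test of preoperative against postoperative scores. Its only P-value threshold is "P values below 0.05 will be considered statistically significant", with no exception for any hypothesis. Significance also enters an acceptance rule: "A significant reduction in the BARF scores by 1 face in such patients will be accepted as construct validation".

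**The concern.** A power statement holds only for the level at which the test is run. G1's 90% is tied to 0.01, and G2 runs the same tests at 0.05, so the quoted power is not the power of the planned analysis. The protocol does not reconcile the two: it has no multiplicity adjustment, and nothing says that 0.01 was for planning only. G1's remark about being conservative does not mention the significance level.

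The level might matter because G2 accepts construct validity on a significant fall in BARF scores, and validity in Spanish-speaking children is the first aim. Hypothesis 1 is tested only in children rescued in the PACU, and the protocol gives neither a rescue rate nor an SD for BARF changes. A result with p between 0.01 and 0.05 would pass under G2 and fail at the level used in G1.

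**Working it through.** **Inputs.** From G1: difference 2.0 cm, SD 2.5 cm, 27 children, 90% power, level 0.01, 240 recruited, 10% loss. From G2: level 0.05. Assumed here: a two-sided paired t-test, with 2.5 cm as the SD of the differences. If 2.5 cm is the SD of a single score, the SD of differences is 2.5 × √(2(1 − ρ)), which equals 2.5 cm at a before/after correlation ρ of 0.5.

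**1. G1's figure.** The standardised effect is 2.0/2.5 = 0.8. With n pairs the noncentrality is 0.8√n; for n = 27 it is 4.16. The two-sided 0.01 critical value on 26 df is 2.779, and the noncentral t gives power 0.905. With 26 pairs it is 0.890. So 27 is the smallest number reaching 90%, and the 0.01 does not look like a misprint. One-sided 0.01 would need only 24. A one-sided two-group normal formula at 0.05 also gives 27 per group: 2 × (2.5/2.0)² × (1.645 + 1.282)² = 26.8. That route contradicts the level G1 states, so the paired reading is the more natural one.

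**2. The same 27 pairs at G2's level.** The critical value is 2.056 and power is 0.979. Nineteen pairs give 0.909 and 18 give 0.892.

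**3. Sensitivity to the SD reading.**

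| ρ (assumed) | SD of differences | Power at 0.01 | Power at 0.05 |
|---|---|---|---|
| 0.25 | 3.06 cm | 72.6% | 90.4% |
| 0.50 | 2.50 cm | 90.5% | 97.9% |
| 0.75 | 1.77 cm | 99.8% | >99.9% |

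Throughout this range, testing at 0.05 keeps at least the 90% that G1 promises.

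**4. The planned rank tests.** In simulations of normal data (20,000 each), the Wilcoxon test with 27 pairs has power 0.890 at 0.01 and 0.975 at 0.05. For the between-group part of hypothesis 2, 240 × 0.9 = 216 children remain. If 27 are rescued (27/216 = 12.5%, an assumption), the split is 27 against 189:

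| Split | t-test, 0.01 | t-test, 0.05 | Mann-Whitney, 0.01 | Mann-Whitney, 0.05 |
|---|---|---|---|---|
| 27 v 189 | 90.0% | 97.2% | 87.4% | 96.4% |
| 27 v 27 | 60.6% | 82.2% | 57.6% | 79.8% |

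The equal split is not planned, since rescued children are compared with all the others; it shows only how the level affects a small comparison.

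**5. When would the level change the verdict?** The observed t is (mean fall/SD) × √n.

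- *Smaller effect.* With 27 pairs and SD 2.5 cm, the limits are 2.056 × 2.5/√27 = 0.99 cm and 2.779 × 2.5/√27 = 1.34 cm. A fall between them passes at 0.05 only. A 2 cm fall has t = 4.16, p = 0.0003.
- *Fewer rescued children.* For a 2 cm fall with SD 2.5 cm, p = 0.043 with 9 children, 0.0104 with 14 and 0.0079 with 15. So 9 to 14 rescued (4.2% to 6.5% of 216) falls between the levels.
- *More variable BARF changes.* With 27 pairs, a 1-face mean fall lies between the levels if the SD of change is from √27/2.779 = 1.87 to √27/2.056 = 2.53 faces. If 1 face corresponds to 2 cm (an assumption suggested by G1 pairing the two as the important change), the SD is 2.5/2 = 1.25 faces and the fall is significant at both levels.

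**The case for a change.** The best case for a change is that one sentence would remove a real inconsistency before any data are seen. The level belongs to an acceptance rule for the study's first aim; it can decide the outcome in the three situations just listed; and the missing rescue rate and BARF SD mean that none of them can be excluded. It may also be that 0.01 was meant as the testing level, in which case G2 is too lenient.

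Part of this stands: the levels differ, the difference is unexplained, and the figures reproduce. But outcomes that depend on the level do not show that the level is wrong. Any threshold has results just either side of it, and G2 says which one applies. G1 answers the form's question about why the sample size was chosen; G2 sets the decision rule. Nothing in the text supports 0.01 as the testing level.

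The two available edits do not improve matters. Restating G1 at 0.05 would change no test and no result. Moving G2 to 0.01 would cost power: with 14 pairs the Wilcoxon test would drop from 78% to 48%, and 27 pairs from about 97% to 89%. That would be a trade-off for the investigators, not the correction of an error.

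**Conclusion.** The mismatch is real but harmless, and the plan can stand. G1's 90% at 0.01 is a true statement on a paired-t reading, and G2's 0.05 is a conventional, unambiguous testing rule. Followed as written, the study tests hypothesis 1 and the paired part of hypothesis 2 with about 98% power if 27 children are rescued, against the 90% claimed. This rests on 2.5 cm being close to the SD of differences; at an assumed before/after correlation of 0.25 the power at 0.05 is still about 90%. How many children will be rescued is not known from the protocol, but that uncertainty exists at either level and is worse at 0.01. Hypothesis 3 is sized on the width of a confidence interval, so its 0.01 does not conflict with a P-value rule. Analysts would apply 0.05 and read 0.01 as a planning margin; a note to that effect is optional.
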